Rationale for Number of Patients	
This is a 1:1 randomised controlled trial in men with metastatic castrate-resistant prostate cancer (MCRPC). Eligible, consented participants will be randomised with equal probability to one of two intervention regimens: supervised exercise (SE) group for 48 weeks (12 x 28-day cycles) which tapers progressively to self-management with psychosocial support or psychosocial support for men in the self-directed exercise (SDE) group. Men will be stratified by treatment status at the time of randomization and site.
 
Considering a total enrolment period of 60 months and minimum 36 months follow-up for each patient after enrolment; assuming survival time follows an exponential distribution; and assuming a median OS survival of 33.5 months in the control arm, the sample size required to detect a hazard ratio (HR) of 0.78 with 80% power at significance level of 0.05 is 824 translating to 412 men in each arm. Accounting for 5% of patients with unknown survival status at 3 years, we aim to enrol 866 men.
 
With 80% power, we will observe median survival times (>216 events in both arms) at 66 months (5.5 years) after the first enrolment.

Statistical Analysis Plan for Primary Endpoint	An intent-to-treat approach will be used to analyse OS. Patients without death at the end of follow-up will be censored on the date of the last contact (or, if no contact after baseline, at the date of randomisation + 1 day). Kaplan-Meier methods will be used to estimate the median OS for each treatment arm as well as the 1-year, 2-year, and 3-year OS rates and corresponding 95% confidence intervals. A two-sided log-rank test stratified by treatment status at the time of registration (Y/N) and study site will be used to assess the effect of the intervention. Un-stratified log-rank tests will be examined as sensitivity analyses. Cox proportional-hazard regression models will be used to estimate the hazard ratio and its 95% confidence interval to quantify the effect of the intervention on OS, adjusting for stratification factors and other potential confounding factors.

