Duration of Patient Participation and Duration of Study	All patients will be followed for OS a minimum of 36 months (for those men enrolled last during the 3 year enrolment period) after randomisation to observe median survival time in both groups. After the intervention period, participants will complete a set of surveys on a yearly basis; we will contact them, then next of kin and alternate contact, if needed, if we do not hear from them.

LIST OF ABBREVIATIONS

ADT	androgen deprivation therapy
AE	adverse event
ALP	alkaline phosphatase
ALT	alanine aminotransferase
ANC	absolute neutrophil count
AR	androgen receptor
AST	aspartate aminotransferase
BICR	blinded independent central review
BMI	body mass index
BPI-SF	Brief-Pain Inventory Short Form
BUN	blood urea nitrogen
CFR	Code of Federal Regulations
CNS	central nervous system
CPET	cardiopulmonary exercise test
CR	complete response
CRF	case report form
CRP	c-reactive protein
CRPC	castration-resistant prostate cancer
CT	computed tomography
CTCAE	Common Terminology Criteria for Adverse Events
CVA	cerebrovascular accident
ECC	Exercise Coordinating Centre
ECG	electrocardiogram
ECOG	Eastern Cooperative Oncology Group
FACT-P	Functional Assessment of Cancer Therapy-Prostate
FACIT	Functional Assessment of Chronic Illness Therapy
FFPE	formalin-fixed paraffin-embedded
FFQ	food frequency questionnaire
GnRH	gonadotropin-releasing hormone
EQ-5D	EuroQOL five dimension questionnaire
GCP	good clinical practice
HDL	high density lipoprotein
HIIT	intensity interval training
HIPAA	Health Insurance Portability and Accountability Act
HPFS	Health Professionals Follow-up Study
HR	hazard ratio
HRmax	maximum heart rate
ICH	International Conference on Harmonisation
IDMC	Independent Data Monitoring Committee
IEC	Independent Ethics Committee
IGF-1	Insulin-like growth factor-1
LDL	low density lipoprotein
IL-1β	Interleukin-1 beta
IL-2	Interleukin-2
IL-6	Interleukin- 6

IV	intravenous
IRB	Institutional Review Board
LHRH	luteinizing hormone-releasing hormone
LPI	last patient in
M-CRPC	metastatic castration-resistant prostate cancer
MI	myocardial infarction
MRI	magnetic resonance imaging
NCI	National Cancer Institute
NFκb	nuclear factor kappa-light-chain-enhancer of activated B cells
Nrf-2	nuclear factor erythroid 2-related factor 2
OS	overall survival
PCWG	Prostate Cancer Clinical Trials Working Group
PDWG	Protocol Development Working Group
PET	positron emission tomography
PFS	progression-free survival
PR	partial response

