10.0 PRIMARY ENDPOINT CRITERIA FOR OVERALL SURVIVAL

Patients will be followed for death a minimum of 36 months after randomisation. Overall survival will be measured from the time of randomisation until death. Medical records and death certificates will be reviewed every 6 months to obtain survival status. Country-specific mortality status databases will also be searched annually; cause of death will be determined through review of medical and death records. Patients will be contacted once a year, and follow up with next of kin then alternate contact, if needed, if we do not hear from them.

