12.2 Power and Sample Size for Primary Endpoint

This is a 1:1 randomised controlled trial in men with MCRPC. Registered and eligible participants will be

randomised with equal probability to one of two intervention regimens: supervised exercise for 12 cycles tapering to self-management for 12 cycles with psychosocial support or psychosocial support alone. We will stratify by whether the men are on active therapy or not at the time of registration (yes/no) and study site. A total of 866 men will enrol in this study to ensure at least 412 men evaluable for OS in each arm.

Null hypothesis (H_0)= There is no difference in OS between patients randomised to the exercise intervention plus psychosocial support vs psychosocial support alone.

Alternate hypothesis (H_A) = There is a difference in OS between patients randomised to the exercise intervention plus psychosocial support vs psychosocial support alone.

Considering a total enrolment period of 36-months and minimum 36 months follow-up for each patient after enrolment; assuming survival time follows an exponential distribution; and assuming a median OS survival of 33.5 months in the control arm, the sample size required to detect a hazard ratio (HR) of 0.78 with 80% power at significance level of 0.05 is 824, 412 men in each arm. Accounting for up to 5% of patients with missing data on OS, we aim to enrol 866 men. If we consider non-compliance of 10% in the intervention arm, which equates to 371 patients in the intervention arm who are compliant, this provides 77.7% power to detect an HR of 0.78, when comparing the 371 compliant patients with the 412 patients in the control arm at the significance level of 0.05.

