12.4 Analysis of Primary Endpoint

The primary endpoint for the study is OS (defined in Section 10). An intent-to-treat approach will be used to analyse OS. Patients alive at the end of follow-up will be censored on the date of last contact (or, if no contact after the baseline visit, at the date of randomisation + 1 day). Kaplan-Meier methods will be used to estimate the median OS for each treatment arm as well as the 1-year, 2-year, and 3-year OS rates and corresponding 95% confidence intervals. A two-sided log-rank test, stratified by treatment status (on treatment Y/N) and study site, will be used to assess the effect of the intervention. Un-stratified log-rank tests will be examined as sensitivity analyses. Cox proportional-hazard regression models will be used to estimate the hazard ratio and its 95% confidence interval to quantify the effect of the intervention on OS, adjusting for stratification factor(s). First, the base model will be evaluated and then other potential confounding factors will be considered. We will also conduct secondary analyses with consideration for non-compliance and the number of supervised sessions completed.

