We will complete this interim analysis when the first 130 patients complete 1RM and 400m walk testing on or within 7 days *after* Cycle 6, Day 1 (6 months after Day 1 of the intervention), and estimate the mean difference between the groups for both the 400m walk and leg extensions. [name] data is pilot data based on small sample sizes, so we have attenuated the expected effect size for these two parameters to 0.40; however, we will revisit the comparison when a larger dataset is available. We will consider an analysis similar in scope to this example: Assuming that the standard deviation of change in 400m walk is 8.75 and leg extension is 5.16 (based on preliminary data above), if the difference in leg extension strength between the two arms is less than 2.06kg *or* the difference in the 400m walk between the two arms is less than 3.5 seconds we will consider modifications to the protocol.

Analysis 2: Efficacy and possible early termination due to unequivocal results

The interim analysis plans to investigate the primary outcome when half of the required number of events for final analysis of overall survival (i.e., 315 events) will be carried out with $\alpha=0.0005$. A stringent alpha level has been chosen to reduce the amount of alpha spending prior to the final analysis with the full sample. The interim analyses will spend 0.001 of the 0.05 alpha requiring us to reach $0.05-0.001 = 0.049$ for the final trial results to be considered statistically significant with an overall $\alpha=0.05$.

The interim analysis will be carried out to assess whether the study should terminate early due to an unequivocal result at the 0.0005 level. This interim analysis can result in recommendations that include modifications to the study, including termination of accrual, modifications to data collection, or early reporting of results. Recommendations will be made to the Steering Committee, who will make the final decisions.

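### The overall survival interim at 315 deaths is called half of the required number, but the plan's own design inputs need about 510 deaths, and no section states the final count

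*Combined protocol and SAP*

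**What the plan says.** Section 12.12, Analysis 2, schedules the efficacy interim "when half of the required number of events for final analysis of overall survival (i.e., 315 events"). It spends 0.001 of the alpha there and leaves 0.049 for the end.

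The design inputs are in Section 12.2: "the sample size required to detect a hazard ratio (HR) of 0.78 with 80% power at significance level of 0.05 is 824", with exponential survival, a control median of 33.5 months and 1:1 allocation. Enrolment is set at 866 to allow for 5% missing survival status. Section 12.4 specifies the test: "A two-sided log-rank test, stratified by treatment status (on treatment Y/N) and study site".

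No section gives the number of deaths required for the final analysis. The only other event count is in the synopsis (Rationale for Number of Patients), "we will observe median survival times (>216 events in both arms) at 66 months", and it describes when the medians are observed. Section 17.6 ends the trial when the survival endpoint has been met, without a number. Section 10.0 fixes follow-up by time: "Patients will be followed for death a minimum of 36 months after randomisation".

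The calendar is not consistent:

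- Section 12.2: "Considering a total enrolment period of 36-months and minimum 36 months follow-up for each patient after enrolment".
- Synopsis, sample size rationale: "Considering a total enrolment period of 60 months and minimum 36 months follow-up for each patient after enrolment".
- Synopsis, study duration: "for those men enrolled last during the 3 year enrolment period".
- Section 17.6: 5 years of accrual and about 41 months beyond the last patient in, but a total of about 77 months.

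**The concern.** The interim count is a decision figure: it determines when the monitoring committee sees survival data by arm. If it is half of the required number, that number is 630. The stated hazard ratio, power and alpha point to a number near 510. With no final count stated anywhere, the doubled interim figure is the only clue to the final target, and it disagrees with the sample size section. At stake are the description of how much information the interim carries and the definition of when the final analysis is run.

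**Working it through.** **Inputs.** Hazard ratio 0.78, power 80% (z = 0.8416), alpha 0.05 (z = 1.9600), control median 33.5 months, exponential survival (Section 12.2); two-sided log-rank test (Section 12.4); final alpha 0.049 (z = 1.9686, Section 12.12). Assumed: uniform accrual and no dropout.

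**1. Required deaths.**

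- Schoenfeld, 4(z_a + 0.8416)² / (ln 0.78)²: 508.6 at alpha 0.05 and 511.7 at 0.049.
- Freedman, (z_a + 0.8416)² × (1.78/0.22)²: 513.8 at alpha 0.05 and 517.0 at 0.049.

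Rounded up, these are 509 and 514 at 0.05, and 512 and 517 at 0.049.

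**2. Reproducing the plan's 824.** With accrual A and further follow-up F, the death probability at hazard λ is 1 − [exp(−λF) − exp(−λ(A+F))]/(λA). For A = F = 36 this is 0.665 in the control arm and 0.576 in the exercise arm, mean 0.6205. Then 509/0.6205 gives 821 men and 514/0.6205 gives 829, either side of 824. Conversely, 824 × 0.6205 = 511 deaths. The stated sample size therefore rests on about 510 deaths.

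**3. The interim fraction.** Half of 509 to 517 is about 255 to 259. As a share of required deaths, 315/509 = 61.9%, 315/512 = 61.5%, 315/514 = 61.3% and 315/517 = 60.9%. At hazard ratio 0.78, neither 90% power (681 or 688 deaths two-sided, 555 or 561 one-sided) nor a one-sided 0.05 test at 80% power (401 or 405) gives 630.

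**4. If the final analysis is set by calendar.** Expected deaths at hazard ratio 0.78:

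| Accrual + follow-up (months) | Mean death probability | Deaths, 824 / 866 men | 315 as a share |
|---|---|---|---|
| 36 + 36 | 0.6205 | 511 / 537 | 62% / 59% |
| 36 + 41 | 0.6534 | 538 / 566 | 59% / 56% |
| 60 + 36 | 0.6849 | 564 / 593 | 56% / 53% |
| 60 + 41 | 0.7121 | 587 / 617 | 54% / 51% |

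None reaches 630.

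**5. Power and type I error.** Power is Φ(|ln 0.78|√d/2 − 1.9686): 80.0% at 511 deaths, 86.8% at 617 and 87.5% at 630. For type I error, take limits of 3.2905 at the interim and 1.9686 at the end, with correlation √t between the two statistics. The overall two-sided level is 0.0492 at t = 0.50 and 0.0491 at t = 0.615.

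**6. When 315 deaths occur (hazard ratio 0.78).** With 36-month accrual: about month 44 to 45, after enrolment closes. With 60-month accrual: about month 57 to 59, with roughly 15 to 40 men still to enrol. For 256 deaths the months are 38 to 39 and 51 to 52.

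**7. Chance of stopping.** The probability of crossing the 99.9% efficacy limit at hazard ratio 0.78 is Φ(|ln 0.78|√d/2 − 3.2905): 9.6% at 256 deaths and 13.9% at 315. By symmetry the same figures apply to the 99.9% interval lying wholly above 0.78 when the true hazard ratio is 1.

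**8. Duration.** In Section 17.6, 60 + 41 = 101 months, whereas 36 + 41 = 77.

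**The case against.** The best defence is that 509 to 517 is the minimum for 80% power, while the plan ties follow-up to time and names no event trigger. On 5 years of accrual plus 41 months, with 866 men, 315 is 51% of the deaths expected, so half would be nearly right. That stands as a limit on the point: 61 to 62% is the share of required deaths and need not be the information fraction at a calendar-driven final analysis. It does not rescue the sentence, which speaks of the required number.

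A reader might infer more than the documents support:

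- **That the error inflates type I error or costs power.** It does neither. The overall level stays near 0.049, and every schedule in the table gives at least 80% power.
- **That the source of 315 is known.** Deaths expected with no effect in 866 men over 60 + 36 months are 630.5, half of which is 315. But the Schoenfeld number for hazard ratio 0.80 at 80% power is also 630.5. The origin is unknown.
- **That 315 is itself the final number.** The sentence is awkward enough to allow this, but 315 deaths would give only about 60% power.
- **That the accrual conflict decides whether the interim could still stop randomisation.** Even on 60-month accrual, 315 deaths arrive only 1 to 3 months before enrolment ends, under an assumed uniform accrual. On either calendar the look falls near or after the end of enrolment. Early reporting and changes to data collection remain possible.

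The synopsis (Data Monitoring Committee) also lets the committee chair schedule further interims, so this is the only planned look at survival, not the only possible one.

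**Conclusion.** The description of 315 as half of the required deaths is wrong on the plan's own inputs: it is about 61 to 62% of the 509 to 517 needed. Against calendar-based expected deaths it is about 51 to 62%. The more consequential gap is that the final death count is never stated, which leaves about 512 deaths (80% power) and 630 (about 87%) both open. The required number follows from the stated hazard ratio, power and alpha and does not depend on the accrual calendar. The expected counts and timings rest on exponential survival, uniform accrual and no dropout.

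This should be fixed, but it is a correction of text and does not threaten the validity of the test. The accrual and duration conflict is real and secondary.

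So is a wording fault in Analysis 2. It applies statistical significance at p < 0.001 to an interval that excludes only a 22% mortality reduction; such an interval rejects 0.78, not 1. It then restates the futility limb as a 22% gain in survival. Under exponential survival a hazard ratio of 0.78 lengthens the median from 33.5 to 42.9 months (1/0.78 = 1.28), whereas a 22% gain corresponds to 1/1.22 = 0.82. Later sentences there separate the two consequences and leave the decision to the Steering Committee, so this is a matter of wording.

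**What to change.** 1. State the required number of deaths in Sections 12.2 and 12.12 (about 512 by Schoenfeld at alpha 0.049), and say whether the final analysis is triggered by events or by calendar time.
2. Either keep 315 and describe it as about 62% of required deaths, or set the look at about 256. Keeping 315 costs only a less round fraction. Moving to 256 brings the look forward by about 6 to 7 months and lowers the chance of crossing the efficacy limit at hazard ratio 0.78 from 14% to 10%, with the same fall in the chance of meeting the futility limb at hazard ratio 1.
3. Reconcile accrual and duration across the two synopsis entries, Section 12.2 and Section 17.6 (36 or 60 months; 77 or 101 months in total), and acknowledge that a look at 315 deaths falls near or after the end of enrolment.
4. In Analysis 2, reserve the significance statement for intervals that exclude a hazard ratio of 1, and express futility by one criterion: the 99.9% lower limit for the hazard ratio above 0.78.

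The 99.9% interval and the 0.001/0.049 split can stay. No extra patients and no alpha are needed; the changes should be made before the interim is triggered.

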12.13 Additional Analyses

12.13.1 Health Economic Evaluation

An economic evaluation will be performed in parallel to the trial in order to assess the health benefits, additional costs, and potential savings of including exercise therapy as standard of care for men with mCRPC.

The cost analysis will follow international accepted guidelines for undertaking economic evaluation. Thus, the cost analysis will adopt a three-step process involving the identification, measurement, and valuation of the resource use (costs) associated with the delivery of the intervention, compared to the control group. Clinical data will be supplemented with patient and site information to measure the use of highly relevant clinical services and resources. Costs will be valued using appropriate country costs and will be converted into International dollars using purchasing power parity estimates.

13.0 ADVERSE EVENTS AND REPORTING REQUIREMENTS

Adverse events (AEs) will be graded according to the NCI Common Terminology Criteria for Adverse Events (CTCAE) Version 4.0 and coded. Adverse events shall be assessed at every cycle and the following details recorded on the CRF: type, severity, relationship to exercise intervention and disease, expectedness, SAE (yes/no), timing, action taken (if any) and outcome.

13.1 Definitions

13.1.1 Clinical Adverse Events (AE)

A clinical adverse event is any unfavourable or unintended sign, symptom, or disease temporally associated with the study intervention and occurring in a patient assigned to the intervention. All AEs reported from the date of informed consent until 28 days after the Off-Study visit will be considered. AEs are assessed by the exercise physiologist, trainer, etc. at on-site exercise visits and in all subjects (in person or by phone) on a monthly basis. This includes adverse clinical or laboratory findings, illness, or an exacerbation or progression of a disease/condition present at baseline. A list of standard questions will be used to assess any AEs, provided in the SOM.

In this trial, the study intervention is defined as supervised aerobic and resistance exercise. All potential participants will be screened via their medical charts as well as through in-person assessments to assess cardiovascular contraindications to exercise. Our multi-gated comprehensive approach should systematically identify and screen out any individual for whom this study is contraindicated.

However, rare but serious AEs are possible. Those that may occur during either cardiopulmonary exercise testing (CPET) or exercise training include myocardial infarction (heart attack), stroke, unconsciousness or other serious injury.

- Events during a CPET are rare (<1/100,000 in well individuals and 1/10,000 in sick individuals). A trained health professional (e.g. medical staff and exercise physiologist) will monitor the exercise test in a location staffed by physicians, in the rare event that such an event occurs.
- Similar to a CPET, exercise training may cause temporary risks of an adverse cardiovascular event, such as a heart attack. The CPET with ECG-monitoring that must be completed prior to randomisation will ensure that all randomised participants are healthy enough to engage in exercise training.

Absolute and relative indications for stopping exercise (both testing and training) are provided in [Table 5](#). In the event of a participant presenting with any of the below symptoms exercise should be stopped.

Table 5. Indicators for Stopping Exercise

Absolute indications for Stopping Exercise:

- Suspicion of a myocardial infarction or acute myocardial infarction (heart attack)
- Onset of moderate-to-severe angina (chest pain)
- Drop in systolic blood pressure (SBP) below standing resting pressure or drop in SBP with increasing workload accompanied by signs or symptoms
 - Hypotensive response resulting in SBP <60mmHg
- Signs of poor perfusion (circulation or blood flow) including pallor (pale appearance to the skin), cyanosis (bluish discoloration) or cold and clammy skin
- Severe or unusual shortness of breath
- CNS (central nervous system symptoms)
 - Ataxia (failure of muscular coordination)
 - Vertigo (an illusion of dizzying movement)
 - Visual or gait (pattern of walking or running) problems
 - Confusion
- Patient's request to stop
- Irregular pulse
- Extreme fatigue
- Skeletal fracture
- Increased bone pain

Relative Indications:

- Increasing chest pain
- Physical or verbal manifestations of shortness of breath or severe fatigue
- Wheezing
- Leg cramps or intermittent claudication (grade 3 on a 4-point scale)
- Hypertensive response

Other examples of AEs include but are not limited to:

- Abnormal test findings (see specific criteria for AE reporting, below)
- Clinically significant signs and symptoms
- Changes in physical examination findings

- Worsening of signs and symptoms of the malignancy under study. Disease progression assessed by measurement of malignant lesions on radiographs or other methods **should not** be reported as an adverse event, unless the outcome is fatal during the study or within the safety reporting period (up to 28 days after the 24th cycle) – see definition of serious adverse event below.
- Signs or symptoms resulting from exercise overload
- Drug interactions

For laboratory abnormalities, the criteria for determining whether an abnormal test finding should be reported as an adverse event are as follows:

- Test result is associated with accompanying symptoms, and/or
- Test result requires additional diagnostic testing or medical/surgical intervention, and/or
- Test result leads to a change in study dosing outside of protocol-stipulated dose adjustments or discontinuation from study, significant additional concomitant treatment, or other therapy, and/or
- Test result is considered to be an adverse event by the Investigator

